performed as a reference. Tumor response will be evaluated by RECIST 1.1 criteria and secondarily by irRECIST criteria. The overall response rate will be summarized by frequency counts and percentage, and will be tested by Fisher's Exact test. PFS is defined as the time from randomization until objective tumor progression or death. Subjects who have not progressed or died will be censored for the analysis. Kaplan-Meier (KM) curves and descriptive statistics will be used to summarize PFS. The percentage of subjects with PFS and the 95% confidence intervals will be provided. PFS and duration of response will be summarized using KM method and tested by the Log-Rank test controlled by disease type.

Furthermore, disease response will be tabulated for all subjects who receive ADXS11-001 monotherapy, MEDI4736 monotherapy, or ADXS11-001 + MEDI4736 combination therapy.

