3.4 Part B - Primary Objectives & Hypothesis

Objective: To evaluate tumor response and PFS by RECIST 1.1 and irRECIST of ADXS11-001 and MEDI4736 administered as monotherapy and in combination.

Objective: To evaluate the safety and tolerability of ADXS11-001 administered in combination with MEDI4736 by NCI CTCAE v 4.03.

Hypothesis: ADXS11-001 and MEDI4736 will demonstrate signs of clinical activity.

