5.4 Stratification

In Part B, all 3 treatment arms will be stratified by disease (SCCHN or cervical cancer).

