8.0 STATISTICAL ANALYSIS PLAN

8.1 Statistical Analysis Plan Summary

This is a Phase 1-2 study of ADXS11-001 or MEDI4736 alone or combination in locally advanced, or metastatic, squamous or non-squamous carcinoma of the cervix or HPV+ squamous cell carcinoma of the head and neck.

There are 2 phases in this study with different objectives. For safety, the analysis will be performed for Part A and Part B separately and combined. The efficacy analysis will be performed for Part A and Part B separately. SAS 9.2 or higher will be used for data analysis.

Subject disposition, demographic and baseline subject characteristics will be summarized separately for Part A and Part B. Adverse events will be classified and summarized by type, incidence, severity, and causality. All adverse events will be summarized by subject, treatment, and disease. All subjects who receive at least 1 dose of study treatment will be included in the safety analyses.

Statistical analysis for efficacy will be summarized by treatment arm and disease type. Although it may lack statistical power, statistical testing for treatment comparisons will be performed as a reference. Tumor response will be evaluated by RECIST criteria and secondarily by irRECIST criteria. The overall response rate will be summarized; frequency counts and percentage and will be tested by the Fisher's Exact test. PFS is defined as the time from randomization until objective tumor progression or death. Subjects who have not progressed or who are still alive at the time of evaluation will be censored for the analysis. Kaplan-Meier (KM) curves and descriptive statistics will be used to summarize PFS. The percentage of subjects with PFS and the 95% confidence intervals will be provided. PFS and duration of response will be summarized using KM method and tested by the Log-Rank test controlled by disease type.

Furthermore, the disease response will be tabulated for all subjects who receive ADXS11-001 monotherapy, MEDI4736 monotherapy or ADXS11-001 + MEDI4736 combination therapy.

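### Response rate, a Part B primary objective, has no confidence interval and a test that ignores the randomisation stratum; duration of response gets a between-arm test that only responders can enter

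*Combined protocol and SAP*

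**What the plan says.** Section 3.4 sets the Part B primary efficacy objective: "To evaluate tumor response and PFS by RECIST 1.1 and irRECIST of ADXS11-001 and MEDI4736 administered as monotherapy and in combination". The attached hypothesis is "Hypothesis: ADXS11-001 and MEDI4736 will demonstrate signs of clinical activity".

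Section 5.4 states that in Part B "all 3 treatment arms will be stratified by disease (SCCHN or cervical cancer"). Section 5.3 gives 1:1:2 allocation, and the Section 1.0 summary gives 48 Part B subjects.

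For response, Section 8.1 says "The overall response rate will be summarized; frequency counts and percentage and will be tested by the" Fisher's exact test. Section 2.2 has the same rule: "The overall response rate will be summarized by frequency counts and percentage, and will be tested by Fisher's Exact test".

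The only interval sentence in Section 8.1 concerns PFS: "The percentage of subjects with PFS and the 95% confidence intervals will be provided". The next sentence reads "PFS and duration of response will be summarized using KM method and tested by the Log-Rank test controlled by disease type".

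Two qualifiers in the same paragraph matter. Treatment comparisons are for reference only, with an admission that power may be lacking, and efficacy is to be summarised by arm and by disease type. No alpha, sidedness, effect size or power is given. Duration of response has no definition, start point or censoring rule.

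**The concern.** There are three linked gaps.

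- **No interval for response.** A hypothesis about signs of activity is most naturally judged by how well each arm's response rate is estimated. With 12, 12 and 24 subjects, a bare percentage conceals wide uncertainty, and a between-arm p-value does not fill the gap.
- **The test ignores the stratum.** Disease type is used to randomise and to control the log-rank tests, but not to test response. If response differs by disease, power is lost.
- **Duration of response is tested between arms.** Only responders have a duration. Responder status is determined after randomisation, so the comparison is not protected by it and can mislead in either direction. Very few subjects would contribute.

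At stake is how far readers can interpret a primary endpoint, and whether a p-value from a handful of responders is quoted as evidence. No confirmatory decision depends on it.

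**Working it through.** **The plan's own figures.** 18 + 48 = 66, matching the stated total. 48 at 1:1:2 gives 48/4 = 12, 48/4 = 12 and 48/2 = 24. There is no stated power or precision to reproduce.

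**Assumptions, not in the documents.** The response rates below; a 50:50 disease mix (6 v 12 in each disease) unless stated; two-sided 5%; and a pairwise contrast of the combination (24) with one monotherapy (12). The plan does not say whether Fisher's test is pairwise or across three arms.

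**1. Precision.** Clopper-Pearson limits for x responders of n: lower = Beta quantile 0.025 with parameters (x, n−x+1); upper = Beta quantile 0.975 with parameters (x+1, n−x).

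| Observed | Rate | Exact 95% CI | Width (points) |
|---|---|---|---|
| 1/12 | 8.3% | 0.2–38.5% | 38.3 |
| 3/12 | 25% | 5.5–57.2% | 51.7 |
| 4/24 | 16.7% | 4.7–37.4% | 32.6 |
| 6/24 | 25% | 9.8–46.7% | 36.9 |

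**2. Test size.** All outcomes were enumerated with binomial weights. The stratified exact test conditions on the number of responders in each disease. Its two-sided p-value sums the probabilities of all outcomes no more likely than the one observed. Mid-p counts equally likely outcomes at half weight.

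| True rate in the two diseases, same in both arms | Fisher | Stratified exact | Stratified mid-p |
|---|---|---|---|
| 5% / 35% | 1.6% | 2.3% | 4.5% |
| 10% / 30% | 2.1% | 2.4% | 4.6% |
| 20% / 20% | 2.5% | 2.6% | 4.5% |

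With 5%/45% and a 67:33 disease mix, Fisher's size falls to 1.0%. It does not exceed 5% in any case checked.

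**3. Power, same method.**

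| Monotherapy v combination, by disease | Fisher | Stratified exact | Stratified mid-p |
|---|---|---|---|
| 15/15%, odds ratio 4 | 28.5% | 28.7% | 35.6% |
| 10/10% v 40/40% | 38.7% | 38.9% | 47.6% |
| 5/25% v 30/60% | 36.2% | 39.1% | 47.3% |
| 5/35%, odds ratio 6 (24/76%) | 34.3% | 44.1% | 50.2% |
| 5/45% v 35/80% | 36.4% | 46.6% | 54.0% |

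Stratifying adds 28.7 − 28.5 = 0.2 points at one end and 46.6 − 36.4 = 10.2 at the other. Mid-p adds roughly 6 to 9 more in these rows (50.2 − 44.1 = 6.1; 47.6 − 38.9 = 8.7).

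The two-sided convention matters. If the smaller tail is doubled instead, the stratified test has 37.3% power in the 5/35% row, a gain of only 3.0 points. In the 15/15% row it has 22.6%, below Fisher's 28.5%.

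**4. Duration of response.** At a 15% response rate, expected responders are 12 × 0.15 = 1.8, again 1.8, and 24 × 0.15 = 3.6. The chance that a given monotherapy arm has none is 0.85^12 = 14.2%. For at least one of the two it is 1 − (1 − 0.142)^2 = 26.4%, and no test involving an empty arm can then be run.

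Schoenfeld power is Φ(|ln HR| × √(d × 2/3 × 1/3) − 1.96). At HR 0.5, d = 4 events gives Φ(0.654 − 1.96) = 10%, and d = 12 gives Φ(1.132 − 1.96) = 20%.

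**The case against.** The best defence is that the plan calls its tests reference only, admits that power may be lacking, attaches no alpha or success rule to them, and already displays efficacy by disease type. That stands. It weakens any complaint about lost power, but it makes the missing interval more important, because estimates are then what the trial delivers. Tabulating response by disease supplies neither an interval nor a stratified test.

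Three stronger readings are tempting, and the documents support none of them.

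- **Fisher's test is invalid here.** It is not. Its size stayed below the nominal 5% throughout; the cost is efficiency only.
- **A large power gain is available for nothing.** Going from 34% to 50% needs response rates of 5% and 35% by disease and an odds ratio of 6, which nothing in the documents suggests, and part of that gain is mid-p. With equal rates by disease, stratifying gains almost nothing, and unstratified mid-p does as well as stratified mid-p (35.6% in the 15/15%, odds ratio 4 case).
- **The plan expressly specifies an unstratified test and a responder-only comparison.** It uses neither term. The first is inferred from the contrast with the log-rank sentence in the same paragraph; the second follows from what duration of response is.

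Two further cautions apply. Duration of response is not named in the Part B primary objective, so its p-value carries limited weight. Section 8.1 is also headed as a summary, so a fuller plan could add detail that is not in the document reviewed.

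**Conclusion.** The point holds, and its main part is estimation. A primary-objective endpoint is to be reported without an interval, in arms where an observed 25% carries an exact 95% interval about 52 points wide (12 subjects) or 37 points wide (24 subjects). Those widths depend only on the 12:12:24 split and the observed counts.

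The choice of test is secondary. Fisher's test is valid but conservative, with size 1.6–2.5% in the three main null cases. Stratifying by disease adds about 0 to 10 points of power, depending on how far response differs by disease. That range rests on assumed rates, the assumed disease mix, a pairwise 12 v 24 contrast and the probability-ordering p-value.

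The between-arm log-rank test on duration of response should go. It is not a randomised comparison, and at plausible response rates it would rest on a handful of subjects or could not be run. This is worth correcting, but it does not threaten the trial's validity.

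**What to change.** Amend Sections 2.2 and 8.1 as follows.

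1. Make estimation the main display for response: a Clopper-Pearson 95% CI for the response rate in each arm, and disease-stratified 95% CIs (for example Miettinen-Nurminen) for combination minus each monotherapy.
2. Replace Fisher's test with an exact Cochran-Mantel-Haenszel test stratified by disease. Name the pairwise contrasts and specify the probability-ordering two-sided p-value, since doubling the tail can lose the gain. Mid-p is optional; its downside is that it does not strictly guarantee 5% (4.5–4.6% in the size table above). Keep the reference-only label.
3. Delete the between-arm log-rank test for duration of response. State its start point and censoring rule, and report it descriptively by Kaplan-Meier with the number of responders in each arm. No substitute endpoint is needed.

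The cost is plan wording and standard SAS code. Subjects, visits and data collection are unchanged.

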8.2 Safety Monitoring

An external Data Safety Monitoring Committee will not be established for this study. A periodic safety review will be applied by an internal safety review team with medical capabilities to review individual and summary data collected in the safety and clinical databases. Findings having immediate implication for the management of subjects on study will be communicated to all Investigators in the timeframe associated with unexpected and drug-related SAEs.

9.0 LABELING, PACKAGING, STORAGE AND RETURN OF CLINICAL SUPPLIES

9.1 Investigational Product

The investigator shall take responsibility for and shall take all steps to maintain appropriate records and ensure appropriate supply, storage, handling, distribution and usage of investigational product in accordance with the protocol and any applicable laws and regulations.

9.2 Packaging and Labeling Information

Clinical supplies will be affixed with a clinical label in accordance with regulatory requirements.

9.3 Clinical Supplies Disclosure

This trial is open-label; therefore, the subject, the trial site personnel, the Sponsor and/or designee are not blinded to treatment. Drug identity (name, strength) is included in the label text; random code/disclosure envelopes or lists are not provided.

9.4 Storage and Handling Requirements

Clinical supplies must be stored in a secure, limited-access location under the storage conditions specified on the label.

Receipt and dispensing of trial medication must be recorded by an authorized person at the trial site.

Clinical supplies may not be used for any purpose other than that stated in the protocol.

9.5 Returns and Reconciliation

The investigator is responsible for keeping accurate records of the clinical supplies received from Advaxis or designee, the amount dispensed to and returned by the subjects and the amount remaining at the conclusion of the trial.

Upon completion or termination of the study, all unused and/or partially used investigational product will be destroyed at the site per institutional policy. It is the Investigator's responsibility to arrange for disposal of all empty containers, provided that procedures for proper disposal have been established according to applicable federal, state, local and institutional guidelines and procedures, and provided that appropriate records of disposal are kept.

10.0 ADMINISTRATIVE AND REGULATORY DETAILS

10.1 Confidentiality

The confidentiality of records and information that could identify subjects must be protected, respecting privacy and confidentiality rules in accordance with applicable regulatory requirements.

The Investigator will agree to maintain in confidence all information furnished by the Sponsor and all data generated in the study, except as provided or required by law, and will

divulge such information to the IRB/IEC with the understanding that confidentiality will be maintained by the committee.

The identity of all subjects in this study must remain confidential, and only the initials of said subjects will appear on the case record form (CRF). Qualified representatives from the relevant regulatory agencies, the Sponsor, or its agents may inspect the subject/study records. Subject data obtained during the study may be presented in scientific publications, but at no time will subject names be used.

10.2 Compliance with Financial Disclosure Requirements

Financial Disclosure requirements are outlined in the US FDA Regulations, Financial Disclosure by Clinical Investigators (21 CFR Part 54). It is the Sponsor's responsibility to determine, based on these regulations, whether a request for Financial Disclosure information is required. It is the Investigator's/sub Investigator's responsibility to comply with any such request. The Investigator/sub Investigator(s) agree, if requested by the Sponsor in accordance with 21 CFR Part 54, to provide his/her financial interests in and/or arrangements with the Sponsor to allow for the submission of complete and accurate certification and disclosure statements.

The Investigator/sub Investigator(s) further agree to provide this information on a Certification/Disclosure Form, commonly known as a financial disclosure form, provided by the Sponsor or through a secure password-protected electronic portal provided by the Sponsor. The Investigator/sub Investigator(s) also consent to the transmission of this information to the Sponsor in the United States for these purposes.

10.3 Compliance with Law, Audit and Debarment

International Conference on Harmonization (ICH) Guidance on Good Clinical Practice ([GCP] CPMP/ICH/135/95) and the Sponsor require the Investigator to be aware of his/her obligations in the conduct of this study.

Representatives of the Sponsor must be allowed to visit all study site locations periodically to assess data quality and study integrity. On site, they will review study records and directly compare them with the original source documents, discuss the conduct of the study with the Investigator, and verify that the facilities remain acceptable.

In addition, the study may be evaluated by auditors designated by the Sponsor and by government inspectors who must be allowed access to CRFs, source documents, and all other study files. Sponsor audit reports will be kept confidential.

THE INVESTIGATOR MUST NOTIFY THE SPONSOR PROMPTLY OF ANY INSPECTIONS SCHEDULED BY REGULATORY AUTHORITIES AND PROMPTLY FORWARD COPIES OF INSPECTION REPORTS TO THE SPONSOR.

10.4 Compliance with Trial Registration and Results Posting Requirements

Under the terms of the Food and Drug Administration Modernization Act (FDAMA) and the Food and Drug Administration Amendments Act (FDAAA), the Sponsor of the trial is solely responsible for determining whether the trial and its results are subject to the requirements for submission to the Clinical Trials Data Bank, <http://www.clinicaltrials.gov>. Information posted will allow subjects to identify potentially appropriate trials for their disease conditions and pursue participation by calling a central contact number for further information on appropriate trial locations and trial site contact information.

10.5 Quality Management System

By signing this protocol, the Sponsor agrees to be responsible for implementing and maintaining a quality management system with written development procedures and functional area standard operating procedures (SOPs) to ensure that trials are conducted and data are generated, documented, and reported in compliance with the protocol, accepted standards of Good Clinical Practice, and all applicable federal, state, and local laws, rules and regulations relating to the conduct of the clinical trial.

10.6 Data Management

The Investigator or qualified designee is responsible for recording and verifying the accuracy of subject data. By signing this protocol, the Investigator acknowledges that his/her electronic signature is the legally binding equivalent of a written signature. By entering his/her electronic signature, the Investigator confirms that all recorded data have been verified as accurate.

Detailed information regarding Data Management procedures for this protocol will be provided separately.

12.0 SUMMARY OF CHANGES

Section	Page	Revision	Rationale
General		Minor editing, spelling and section placement changes were made throughout to clarify, correct and improve readability	Administrative/clarifications
General	11	Updated description of MEDI4736 in Summary	Align
General		Added language throughout regarding antibiotic use	Align
General		Removed all language regarding [REDACTED] in Part A (Phase 1) of the study	Based on investigator feedback
5.1.1	31	Revised lab eligibility in Table 1	Aligned with current requirement in protocol
5.1.2	34	Updated Exclusion #13	Based on investigator feedback
5.1.2	34	Updated Exclusion #16	Align to update on allowed antibiotics
5.1.2	35	Added Exclusion #18 regarding contraindication to NSAIDS	To clarify required use of NSAIDs per protocol
5.2.1.4	42	Table 3, Treatment Modification Guidelines	Updated for clarity
5.5.2	51	Added sentence regarding Acetaminophen use	Clarification
5.5.2	51	Updated Prohibited Medications list	Clarification
5.6	52	Revised Supportive Care Guidelines	Updated for clarity
5.6.1	52	Added Cytokine Release Syndrome supportive care guidelines	Updated and expanded for clarity
5.7.2	59	Included details of birth control requirement for male subjects	Clarification
6.0	63	Updated all Trial Flow Charts	Clarifications and footnote corrections. Remove tumor biopsies in Part A
7.1.2.13.2	86	Updated Correlative Studies Blood Sampling	Added additional text for clarification
7.1.2.14.1	88	Added detail regarding lab test timing	Clarification
7.1.4.1	90	Include sentence regarding consent signing verse screening	To ensure adequate time for protocol required wash out periods
7.2.5	105	Removed Table 10	Removed duplicate AE evaluation descriptions
8.2	108	Added Safety Monitoring section	Based on investigator feedback

13.0 APPENDICES

13.1 ECOG Performance Status

Grade	Description
0	Normal activity. Fully active, able to carry on all pre-disease performance without restriction.
1	Symptoms, but ambulatory. Restricted in physically strenuous activity, but ambulatory and able to carry out work of a light or sedentary nature (e.g., light housework, office work).
2	In bed <50% of the time. Ambulatory and capable of all self-care, but unable to carry out any work activities. Up and about more than 50% of waking hours.
3	In bed >50% of the time. Capable of only limited self-care, confined to bed or chair more than 50% of waking hours.
4	100% bedridden. Completely disabled. Cannot carry on any self-care. Totally confined to bed or chair.
5	Dead.

* As published in Oken MM et al. Toxicity And Response Criteria Of The Eastern Cooperative Oncology Group. Am J Clin Oncol 5:649-655, 1982. The Eastern Cooperative Oncology Group, Robert Comis M.D., Group Chair.

13.2 Common Terminology Criteria for Adverse Events V4.03 (CTCAE)

The descriptions and grading scales found in the revised NCI Common Terminology Criteria for Adverse Events (CTCAE) version 4.03 will be utilized for adverse event reporting. http://evs.nci.nih.gov/ftp1/CTCAE/CTCAE_4.03_2010-06-14_QuickReference_8.5x11.pdf

13.3 Response Evaluation Criteria in Solid Tumors (RECIST) 1.1 Criteria for Evaluating Response in Solid Tumors

RECIST version 1.1* will be used in this study for assessment of tumor response. While either CT or MRI may be utilized, as per RECIST 1.1, CT is the preferred imaging technique in this study.

* Eisenhauer EA, et al. New response evaluation criteria in solid tumors: Revised RECIST guideline (version 1.1). Eur J Cancer. 2009 Jan;45(2):228-47.

In addition, volumetric analysis will be explored by central review for response assessment.

14.0 ABBREVIATIONS

ADXS11-001	Lm -LLO Immunotherapy for HPV associated diseases
AEs	Adverse Events
APC	Antigen Presenting Cell
CD4	Cytotoxic T cell, effector T cell, Memory T cell
CD8	Helper T cell, Regulatory T cell
CAT	chloramphenicol acetyl transferase
CFU	Colony Forming Unit
CIN	Cervical Intraepithelial Neoplasia
CR	Complete response
CTL	Cytotoxic T lymphocyte
DCR	Disease Control Rate
DLT	Dose limiting toxicity
DTH	delayed-type Hypersensitivity
GGT	Gamma glutyltransferase
GLP	Good Laboratory Practice
GMP	Good Manufacturing Practice
GOG	Gynecologic Oncology Group
HPV	Human papilloma virus
HspE7	Heat Shock Fusion Protein-Based Immunotherapy
IV	Intravenously
IFN	Interferon
LEEP	Loop Electrosurgical Excision Procedure
LFT	Liver Function Test
LLO	Listeriolysin O
Lm	Listeria monocytogenes
Lmdd	An attenuated strain of Listeria monocytogenes with deletions in two genes (dal and dat)
Lm -LLO	Listeria monocytogenes Listeriolysin O
MDSC	myeloid-derived suppressor cells
MHC	Major Histocompatibility Complex
MIC	Minimum inhibitory concentration
MTD	Maximum Tolerated Dose
NCCN	National Comprehensive Cancer Network
NSAID	Non-Steroidal Anti Inflammatory Drugs
PBMC	Peripheral blood mononuclear cell
PR	Partial response
PSA	Prostate-specific antigen
RBC	Red blood cell
RECIST	Response Evaluation Criteria in Solid Tumors
SAE	Serious Adverse Event
SD	Stable Disease
SOC	Standard of Care
TAA	Tumor Associated Antigen(s)
TCR	T-cell receptor

TIL Tumor infiltrating lymphocytes
tLLO Truncated LLO
Tregs Regulatory T cells
wt-*Lm* wild type *Listeria monocytogenes*
